- ¹ If study assessment assessed within 7 days of Cycle 1, Day 1, they do not need to be repeated.
- ² Correlative blood sampling is optional for patients in Arm B except for at screening and at time of visible disease progression.
- ³ For patients assigned to Arm A, research blood will be collected for tumor methylation analysis and other correlative studies on Day 1 of *every* cycle.
- ⁴ For patients assigned to Arm B, research blood will be collected for tumor methylation analysis and other correlative studies at screening and/or Cycle 1 Day 1 and Day 1 of *every third* cycle beginning with Cycle 4 (Cycle 4, 7, 10).
- ⁵ Patients on Arm B can provide this information to study team member over the phone.
- ⁶ Patients on Arm B who opt not to participate in correlative blood sampling may be assessed by their local oncologist for all clinical, laboratory and imaging parameters.
- ⁷ If study assessment was completed within 7 days of noting visible disease progression, they do not need to be repeated.
- ⁸ For Arm A patients, if research blood was collected within one month, it does not need to be repeated. For Arm B patients, if research blood was collected within 3 months, it does not need to be repeated.
- ⁹ Please refer to Appendix A for definition of ECOG performance status.
- ¹⁰ Radiologic imaging of chest/abdomen/pelvis (CT preferred, abdominal/pelvis MRI will be performed for patients with CT contrast allergy) and any other imaging required per RECIST for the particular subject are required at baseline must be obtained within 4 weeks of initiation of therapy.
- ¹¹ Assessment for presence of visible disease will occur prior to every third cycle, beginning with Cycle 4 (Cycles 4, 7, 10). For each individual patient, the same imaging modality should be used at assessment as was used during screening.
- ¹² Obtain a urine or serum pregnancy test at screening no more than 7 days prior to dosing on Day 1.
- ¹³ Tumor biopsies will be obtained at the time of visible disease recurrence for all subjects. Location of biopsy can be primary tumor or site of metastatic disease, as determined by the treating oncologist. Tumor biopsy may be obtained within 4 weeks of visible disease progression or before first dose of chemotherapy, whichever occurs latest.
- ¹⁴ Completed only if FACIT data not collected at time of visible disease progression

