2.2 Schedule during Follow Up – All Subjects*

Assessments are to be completed within 3 months of safety assessment/progression/previous follow-up

Schedule variations for CA19-9 and Imaging assessments permitted

Procedure *	Follow Up (Until 2 nd disease progression)	Survival Follow-Up ^{**} (≤ 3mo of previous follow up)
Information on new cancer therapies (records to be obtained)	Х	
Subjective response to therapies (records to be obtained)	Х	
CA 19-9 (records to be obtained)	Х	
Imaging completed (records to be obtained)	Х	
Study team contact***	Х	Х

- * For Arm B patients, follow up will be completed within 3 months of cycle 10 or within 3 months of disease progression. For Arm A patients, follow up will be completed within 3 months of safety assessment. If safety assessment was not completed, follow up will begin within 3 months of progression/discontinuation of drug. Follow Up assessments are ideally to be completed on a 3 month schedule, in which subsequent follow ups will be completed within 3 months of the previous follow-up. However, CA.19 and Imaging may be completed per the patient oncologist's discretion. An attempt to contact patients and obtain information on new cancer therapies and subjective responses to such therapies will occur within 3 months of the previous follow up.
- ** Survival Follow-Up will begin once the patient is deemed to have progressive disease for the second time. If the patient has not progressed and was put on Follow Up for reasons other than visible disease progression, patient must still have two instances of visible disease progression until being on the Survival Follow Up schedule. Patients will remain on the selected Follow-Up schedule for a combined total of up to 4 years, death or the subject withdraws consent (whichever occurs first).
- *** Study team will attempt to contact the patient in order to obtain information regarding his/her survival status, and any other comments/information per PI's request. While it is preferred the study team contacts the patient for follow-up, this information may also be obtained through medical records and obituaries.

3 Background and Rationale

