5.1 Overall design

This is a randomized, phase II study of CC-486 versus observation in patients with resected pancreatic adenocarcinoma who have finished adjuvant chemotherapy and/or chemoradiation (or were deemed unable to receive adjuvant therapy) with no evidence of visible disease on imaging and have high risk features. High risk features are defined as an elevated CA 19-9 level > ULN drawn on 2 occasions at least 2 weeks apart; positive nodal disease; and/or positive resection margins. The study will be conducted at Johns Hopkins University, The University of Pennsylvania, Massachusetts General Hospital, and Beth Israel Deaconess Medical Center. Patients will be randomized to one of two arms to enable us to evaluate for effects of CC-486 in this population. Arm A will be started on CC-486 at 300 mg daily for 21 days, repeated every 28 day cycle. The maximum tolerated dose from the phase I trial in patients with MDS, CMML and AML was 480 mg given for 7 days every cycle³¹, however this lower dose given for a prolonged period of time appeared to be tolerated better and had good bioavailability. Arm B will receive observation only. It will be recommended that patients obtain a CA 19-9 and tumor assessment every three months, however, schedule variations are permitted at the oncologist's discretion. Patients on the observation arm who are unable to travel to study site may be followed by their local oncologist ideally adhering to the same schedule. When patients have visible disease recurrence on CT scan, Arm A will stop the CC-486 and may begin their preferred cancer treatment regime. Similarly, after visible recurrence on imaging, Arm B will begin their preferred cancer treatment regime. Both Arm A and Arm B patients will follow the Follow-up schedule after their first visible disease progression. Once patients have had a 2nd instance of visible disease progression, they will be moved to the survival follow-up schedule. We will power this study in order to see a 64% increase of the progression free survival between the two groups. This will require approximately 60 patients to be enrolled and randomized.

5.1.1 5-Azacitidine Description

5-Azacitidine is a pyrimidine nucleoside analog of cytidine. 5-Azacitidine is 4-amino-1- β -Dribofuranosyl-s-triazin-2(1H)-one. The empirical formula is C₈H₁₂N₄O₅. The molecular weight is 244. The structural formula is:

Chemical Structure of 5-Azacitidine

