5.3.2.3 Arm B for the first 12 cycles

Arm B patients will ideally be evaluated (or at the very least contacted by the study team) on Day 1 of every third cycle beginning with Cycle 4.

Patients are permitted to see their local oncologist, and CA19-9 and lesion assessments may be completed outside of the recommended 3 month window (Cycles 4, 7, and 10) at their oncologist's discretion.

Arm B patients will follow a similar schedule as patients in Follow-up, except for a Quality of Life assessment that will be performed.

Correlative blood draw is optional for Arm B patients. If Arm B patients wish, they may have research bloods drawn for correlative studies.

Arm B patients who opt to have research blood collected will have it collected on Day 1 of every third cycle (cycle 4, 7 and 10).

Below is the list of information that must be obtained from Arm B patients.

- Any further therapy received (records to be obtained)
- Subjective response on therapy (records to be obtained)
- Any CA 19-9 drawn (records to be obtained)
- Any imaging (images to be obtained)

Arm B patients will complete a CA 19-9, quality of life assessment and CT scan (or alternate imaging, if clinically indicated) quarterly (ideally).

Arm B patients who are not evaluated in person may have the Quality of Life assessment completed over the [contact] Dose Modification

Table 5.3.1: Arm A: Dose Modification Recommendations for CC-486 Phase
--

Toxicity	Grade	CC-486
Febrile Neutropenia	Grade 3 or 4	Hold until resolved and neutrophils \geq 1500/mm ³
		Restart study drug at 200 mg (two tablets, 33% dose reduction).
		If the same Grade 3 or 4 event recurs (i.e., third occurrence) despite CC-486 dose reduction to 200 mg, as described above, permanently discontinue study
Leukopenia and/or Neutropenia	Grade 2-3Hold dose until recovery to Grade ≤ 1 or baseline.Resume study drug at prior dose	
	Grade 4	Hold until resolved to \leq Grade 1
		Restart study drug at 200 mg (two tablets, 33% dose reduction).
		If the same Grade 4 event recurs (i.e., third occurrence) despite CC-486 dose reduction to 200 mg, as described above, permanently discontinue study drug.
Thrombocytopenia	Grade 1* or 2	Hold treatment until resolution to normal values.
	Grade 3 or 4	Hold until resolved and platelet count ≥100,000/mm ³ Restart study drug at 200 mg (two tablets, 33% dose reduction)
Diarrhea (unresponsive to maximum medical	Grade 1 or 2	Consider administering symptomatic remedies and/or start prophylaxis.

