7.3.4 Measurement of Effect

Response and progression will be evaluated in this study using the new international criteria proposed by the revised Response Evaluation Criteria in Solid Tumors (RECIST) guidelines (version 1.1)⁴⁴. Radiologists are our institution will be interpreting the films and the principle investigator will be determining the type of response or progression using the RECIST criteria.

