11.3 Statistical Methodology

11.3.1 Efficacy Analyses

Progression free survival is defined as the time from randomization until visible recurrence on any imaging modality, a confirmed biopsy, or death. Individuals lost to follow-up prior to having an event will be censored at the time of the last scan or biopsy. In the case of an equivocal scan reading, the patient will be re-imaged on schedule, if clinically appropriate, and if subsequent reimaging confirms recurrence, the event will be considered to have occurred at the first time point when a related abnormality was noted. Overall survival is defined as the time from enrollment until death. Individuals lost to follow-up prior to death will be censored at the time of last physician contact.

Time to event outcomes, including the primary endpoint progression free survival and overall survival, will be summarized using Kaplan-Meier estimates of the survival function. From these estimates, median time to event and one-year survival proportions with 95% confidence intervals will be extracted. Cox proportional hazards models will be used to compare the two treatment arms and to evaluate and adjust for potential prognostic factors (e.g. nodal status, microscopic margins, increase in CA19-9, therapy). The number and type of responses to chemotherapy will be tabulated for each group. Logistic regression will be used to compare the response rate between the groups and to identify risk factors associated with response. Results will be considered statistically significant for p-values < 0.05.

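### In the initial phase only Arm B imaging may be assessed by local oncologists, and the plan never says whose reading sets the PFS date

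*Combined protocol and SAP*

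**What the plan says.** **Who may assess Arm B.** Footnote 6 in Section 2.1 says that Arm B patients who opt out of correlative blood sampling "may be assessed by their local oncologist for all clinical, laboratory and imaging parameters". In the schedule table it is attached to the Arm B tumor-assessment cell and not to the Arm A cell. Section 5.1 opens a second route: "Patients on the observation arm who are unable to travel to study site may be followed by their local oncologist". Section 7.1 leaves Arm B imaging and lesion assessment to the discretion of the patient or oncologist.

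**Who reads.** Section 7.3.4, with no restriction by arm: "Radiologists are our institution will be interpreting the films and the principle investigator will be determining the type of response or progression".

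**What counts as an event.** Section 11.3.1 defines PFS as time from randomization to "visible recurrence on any imaging modality, a confirmed biopsy, or death". No reader is named. Sections 7.1 and 11.3.1 both date a finding that is confirmed later back to when it first appeared or was first noted.

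**What is collected.** Section 5.3.2.3 lists, among the information that must be obtained from Arm B, "Any imaging (images to be obtained". Section 5.5 repeats that item for follow-up but then makes pre-recurrence images optional. Table 2.2 asks only for records of imaging.

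**The concern.** The control arm is observation without placebo, so whoever assesses a scan can know the arm. In a resected abdomen, deciding whether a small change is recurrence takes judgement. The back-dating rule adds to this: the PFS date depends on who first noted something, as well as on who confirmed it.

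If local oncologists make that judgement for some Arm B patients while study radiologists and the principal investigator make it for Arm A, a difference in calling habits cannot be told apart from a drug effect. Earlier local calling shortens Arm B PFS and favours CC-486. Later local calling hides a benefit. Keeping every scan on schedule would not remove the problem, because it concerns who reads the scan and not when it is done.

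**Working it through.** **1. The plan's own figure.** Inputs from 11.3.4 and 11.3.6: 60 patients, medians 6 and 9.84 months (ratio 1.64), one-sided alpha 0.20, 24 months accrual, 12 months minimum follow-up, 10% loss. Taking 10% off gives 54 patients, 27 per arm. With exponential PFS and uniform accrual, the event probability is

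P = 1 − (e^(−12λ) − e^(−36λ)) / (24λ), with λ = ln 2 / median.

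- Median 6: P = 0.915
- Median 9.84: P = 0.793
- Expected events: 27 × (0.915 + 0.793) = 46.1
- Power: Φ(ln(1.64) × √46.1 / 2 − 0.842) = Φ(0.838) = 79.9%

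This matches the stated 80%. The design arithmetic is not in question. It does show that the comparison rests on about 46 events, so a few moved dates matter.

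**2. Effect of a reading difference (assumptions).** The documents give neither the share of Arm B assessed locally nor the size or direction of any reading difference. The illustration assumes that a share f of Arm B events is called one scan (12 weeks, 2.76 months) earlier or later than the study reader would call it. It is a simulation with 27 per arm, control median 6 months, scans every 2.76 months, 24 months accrual, analysis at 36 months, and a log-rank test at one-sided 0.20, with 6,000 replicates.

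| f | False positive, called early | False positive, called late | Power at 1.64, called late |
|---|---|---|---|
| 0 | 20% | 20% | 79% |
| 10% | 23% | 18% | 75% |
| 20% | 26% | 15% | 72% |
| 30% | 29% | 11% | 69% |

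An independent run with 4,000 replicates agreed within about 2 percentage points (early 23/27/29%; late 16/14/11%; power 76/71/70%).

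**3. A second model.** This used 30 per arm, continuous event times and 10,000 runs, with half or all of Arm B shifted. Half called 1 month early gives a false-positive rate of 26%, and 1 month late gives 14%. Half called 2 months early gives 34%, and 2 months late gives 10%. All called 1 month early gives 35%, and 1 month late gives 9%. The direction agrees with step 2.

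**4. How much falls in the asymmetric phase.** Twelve cycles are 48 weeks, about 11.04 months. Under the plan's medians the share still progression-free then is 2^(−11.04/6) = 28% in Arm B and 2^(−11.04/9.84) = 46% in Arm A. So about 72% of Arm B events would fall in the initial phase, and values of f up to 30% fit inside it.

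**The case against.** **The local reading is not said to replace the study reading.** This stands. Footnote 6 says where a patient may be assessed, 7.3.4 has no limit by arm, 5.3.2.3 calls for Arm B images, and 10.3 has the IND sponsor and site investigators review and confirm response assessments. A reader might infer that the sections contradict each other, or that Arm B PFS is certain to be set locally. The documents support neither. They leave open which reading counts. But obtaining an image is not the same as reading it for the endpoint, and the review in 10.3 is not described as a re-read or as blinded. If 7.3.4 covers only RECIST response after recurrence, then no section assigns a reader to the primary endpoint at all.

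**The arms do not have different modality rules.** A reader might infer that they do, from the alternate-imaging wording for Arm B in 5.3.2.3 and from "visible recurrence on any imaging modality" in 11.3.1. The documents do not support it. Footnote 11, under which "the same imaging modality should be used at assessment as was used during screening", is attached to the tumor-assessment cells of both arms. Section 7.3.2 makes CT the default for all patients, the synopsis allows MRI in both arms, and the 11.3.1 wording is common to both. That wording does not need replacing, and dating events later, once CT or MRI shows them, would clash with the back-dating rule.

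**The asymmetry is confined to the initial phase.** This stands. Table 2.2 allows imaging at the oncologist's discretion for all subjects, and Arm A patients enter follow-up when they stop drug.

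**Back-dating already handles late calls.** It does so in part. A lesion noted as equivocal and confirmed later keeps the earlier date, so the late-call figures apply only to lesions that nobody noted at the earlier scan.

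**The magnitudes are assumed.** They are, with every shift one-way and in one arm. At f = 10% the false-positive rate moves by only 2 to 3 points. Deaths, which need no reader, would dilute the effect.

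**Conclusion.** The point holds as an unresolved gap. In the initial phase the plan permits imaging assessment that differs by arm, and it does not say whose reading dates the primary endpoint of an open-label trial. Bias could run either way. On the assumption that 10% to 30% of Arm B events are called one scan early or late, the true one-sided false-positive rate would be roughly 11% to 29% against the nominal 20%. With late calls, power would be 69% to 75% against 79%. The late-call figures are upper bounds on the distortion because of back-dating. None of this shows that bias will occur. The protocol should be changed because the gap is avoidable and cheap to close. Sample size and planned power are unaffected.

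**What to change.** 1. In 7.3.4 and 11.3.1, state that the institutional reading already named in 7.3.4 applies to every scan in both arms, including scans done outside the study sites. Leave treatment arm off the radiology request where feasible. State that this reading alone sets the imaging PFS date, under the existing back-dating rule. Since 5.1 lists four centres, say which institution is meant.
2. In footnote 6, state that local assessment serves to obtain scans and to guide care, and does not set the endpoint.
3. Reconcile 5.5 (pre-recurrence images optional) and Table 2.2 (records only) with 5.3.2.3 (images to be obtained), so that images up to and including recurrence are collected in both arms. Without the earlier images, first appearance cannot be dated by the study reader.

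The cost is protocol wording plus some image transfer and reading time for outside scans. 7.3.4 already names the readers, and 5.3.2.3 already asks for the Arm B images.

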4.2 Endpoints

Primary endpoint

The primary endpoint of the trial is to demonstrate an increase in the progression free survival, PFS, in resected pancreatic cancer patients treated with CC-486

Secondary endpoints

- 1) Response rate (including partial and complete response) to first line chemotherapy when given after visible disease recurrence in patients primed with CC-486 compared to observation
- 2) Overall survival
- **3)** Decreased methylation in candidate genes in the research biopsies as compared to the original resected specimens in patients treated with CC-486.
- 4) Change in quality of life scores as determined by FACIT-Hep

5 Investigational Plan

[figure not shown]

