5.4 Discontinuation of Treatment: Arm A

In the absence of treatment delays due to adverse events, treatment with CC-486 may continue until one of the following criteria applies:

• Interruption of scheduled therapy for greater than four weeks,

- Intercurrent illness that prevents further administration of treatment,
- Adverse event(s) that, in the judgment of the Investigator, may cause severe or permanent harm or which rule out continuation of the treatment regimen
- For any grade 3 and 4 toxicity that recurs despite dose reduction
- Discontinuation of CC-486 for any reason,
- Treatment with other chemotherapeutic or investigational anti-neoplastic drugs,
- Subject decides to withdraw from the study,
- Suspected pregnancy or positive pregnancy, or
- General or specific changes in the subject's condition render the subject unacceptable for further treatment in the judgment of the investigator, or
- Disease recurrence on imaging, or
- Patient has completed one year of therapy with CC-486.

If the subject has visible disease recurrence on imaging or meets any of the aforementioned criteria for removal from study treatment, then the CC-486 or observation phase of this study will conclude and patient will enter the follow-up phase of the study, following the schedule of assessments as described in Section 5.4.2.9.

Mandatory research bloods and tumor biopsies will be obtained at the time of recurrence for both Arm A and Arm B subjects, per the method determined best per the investigator as outlined on the Study Calendar and in Section.

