5.5 Follow-up Phase Both Arms

No disease recurrence:

Less than 10% of patients who have undergone surgery will not develop tumor recurrence after adjuvant therapy.

Therefore, if patients have not recurred after one year of therapy with CC- 486 (Arm A) the drug will be discontinued.

Patients in Arm A will undergo a safety assessment 28 days (\pm 2 days) post the last dose of protocol therapy for resolution of toxicity.

Because Arm B patients do not receive study drug, a safety assessment will not be performed.

All patients (Arm A and B) will be then be contacted (ideally) every 3 months on to obtain the following information about recurrence, survival and anti-cancer treatment (2.2 Study Calendar):

- Any further therapy received (records to be obtained)
- Subjective response on therapy (records to be obtained)
- Any CA 19-9 drawn (records to be obtained)
- Any imaging (images to be obtained)

Disease recurrence

At the time of recurrence, Arm A and Arm B subjects will undergo biopsy of the recurrent lesion per the method determined best per the investigator.

Post recurrence images will be also obtained (pre-recurrence images are optional)

Thereafter, attempts to contact patients every 3 months in order to obtain lesion assessments/post recurrence images, CA19-9 and anticancer treatment and survival information as detailed in section 5.4.2. If study team is unable to make contact with patients, information may be obtained through medical and public records. This information will continue to be collected for patients until patients hit second disease progression.

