8.2.1.2 Archival Tissue

Patients will be consented in order for us to obtain paraffin-embedded blocks and slides of their original resected tumor. This will enable us to perform methylation analysis on the primary tumor and compare this to the tumors at the time of recurrence to determine if treatment with CC-486 led to any changes in methylation. The first slide should be stained for H&E (Hematoxylin and Eosin) for confirmation of the presence of tumor tissue; then, up to 20 serially cut slides should follow. Slides should be 10 microns in thickness and placed in tubes; alternatively, sections may be mounted on charged or silanted slides without coverslips. The H&E stained and all unstained slides will be submitted.

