8.2.1.3 Tumor Biopsies

At the time of recurrence, there must be an attempt to obtain tumor samples by FNA or core biopsy from accessible tumor tissue. A maximum of 8 core biopsies (or fine needle aspirates if cores are considered unsafe) will be obtained from each subject. The aspirates will be used to prepare air dried cytologic smears and frozen samples. The first pass will be used for on-site examination of the material, to determine presence and quality of lesional tissue. The remaining biopsy specimens will be flash frozen in liquid nitrogen and then stored as fresh tissue at \leq -70°C for extraction of DNA and RNA. The biopsy specimens will be stored and evaluated in [name]/ [name]'s laboratory.

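### Footnote 13's biopsy window allows the research sample to be taken after chemotherapy has started, and the methylation analysis does not say how such samples are handled

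*Combined protocol and SAP*

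**What the plan says.** Footnote 13 in Section 2.1 contains two timing statements. The first is "Tumor biopsies will be obtained at the time of visible disease recurrence for all subjects". The second is "Tumor biopsy may be obtained within 4 weeks of visible disease progression or before first dose of chemotherapy, whichever occurs latest".

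The body of the protocol ties the biopsy to recurrence:

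- Section 5.4: "Mandatory research bloods and tumor biopsies will be obtained at the time of recurrence for both Arm A and Arm B subjects".
- Section 5.5: "At the time of recurrence, Arm A and Arm B subjects will undergo biopsy of the recurrent lesion".
- Section 8.2 times the attempted biopsy to visible recurrence in all subjects.
- Section 8.2.1.3: "At the time of recurrence, there must be an attempt to obtain tumor samples by FNA or core biopsy from accessible tumor tissue".

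None of these sections mentions the start of chemotherapy. On treatment after recurrence, Section 5.1 says that "Arm A will stop the CC-486 and may begin their preferred cancer treatment regime"; Arm B has a similar provision. No minimum interval is set, and treatment does not wait for the biopsy.

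Section 8.2.1.2 gives the purpose of the archival tissue: to "compare this to the tumors at the time of recurrence to determine if treatment with CC-486 led to any changes in methylation". Secondary endpoint 3 in Section 4.2 is "Decreased methylation in candidate genes in the research biopsies as compared to the original resected specimens in patients treated with CC-486".

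Section 11.2.2 puts every subject with an evaluable plasma or tumor result into the methylation population. Section 11.3.2 recognises two time points, resection and relapse. It compares change by CC-486 exposure with t-tests, or with Fisher's exact test if change is made binary, and calls the work exploratory.

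**The concern.** The two limits in the footnote do different jobs. The 4-week limit keeps the sample close to recurrence, and the first-dose limit keeps it free of later chemotherapy. Joining them by the later of the two dates removes the second protection whenever chemotherapy begins inside four weeks.

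The recurrence sample is meant to show what CC-486 did. A sample taken after a first-line regimen has begun may reflect that regimen as well, and Section 5.1 leaves the choice of regimen open. The change described in endpoint 3 is measured within CC-486 patients and has no comparator, so any effect of chemotherapy on such a sample could not be separated from the effect of CC-486. The sample also comes from an invasive procedure, with up to 8 cores under Section 8.2.1.3, so it should be interpretable for its stated purpose.

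**Working it through.** The plan gives no figure on this point to reproduce. The check is date arithmetic followed by a comparison of sections.

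**Inputs.** Day 0 is visible progression. The fixed limit is 4 weeks, or 28 days (Section 2.1, footnote 13). Let c be the day of the first chemotherapy dose. The documents do not give c, so the values below are assumptions.

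**Formulas.**
- Last permitted biopsy day as written: max(28, c).
- Days after the first dose on which a biopsy is still allowed: max(0, 28 − c).
- For contrast, last permitted day if the earlier date governed: min(28, c).

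| Assumed c | Last day as written | Days allowed after first dose | Last day if the earlier date governed |
|---|---|---|---|
| 7 | 28 | 28 − 7 = 21 | 7 |
| 14 | 28 | 28 − 14 = 14 | 14 |
| 21 | 28 | 28 − 21 = 7 | 21 |
| 28 | 28 | 0 | 28 |
| 35 | 35 | 0 | 28 |
| 42 | 42 | 0 | 28 |

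The wording therefore permits a biopsy after chemotherapy exactly when chemotherapy starts before day 28. When it starts on day 28 or later, the same wording keeps the biopsy before chemotherapy but extends the window beyond four weeks.

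**Is the situation foreseen?** Section 7.1 prefers imaging within 28 days of starting first-line chemotherapy and allows a repeat scan if treatment is delayed. Starts inside four weeks are thus contemplated, but no frequency is given.

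**Does another section close the gap?** Sections 5.4, 5.5, 8.2 and 8.2.1.3 set the nominal time at recurrence but do not bar a biopsy once chemotherapy has started. Section 11.2.2 excludes no such sample. Section 11.3.2 has no category for it and names no variable for chemotherapy before biopsy.

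**The case against.** Several objections carry weight.

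- **Late sampling is a permission, not the plan.** The footnote's first sentence and the body of the protocol place the biopsy at recurrence. This stands, and it is why the point is one of reconciling a clause.
- **Confounding is not shown.** A reader might infer that the methylation endpoint is confounded. That needs chemotherapy to start before day 28, the biopsy to follow it, and chemotherapy to alter candidate-gene methylation in the sampled tissue. The documents give no frequency for the first two and no direct evidence for the third. The cell-line work in Section 3.3, where azacitidine pre-treatment raised cell death after gemcitabine or docetaxel by 25–30%, makes an interaction conceivable but does not establish one in patients.
- **A difference in time to chemotherapy does not by itself bias the comparison between arms.** Section 11.3.2 contrasts change with and without CC-486 exposure. Bias there requires post-chemotherapy sampling, the regimen, or the regimen's effect to differ by arm.
- **Adjuvant therapy already lies between the two samples** for most patients (Section 5.2.1, criterion 5), so the paired change is mixed in any case. This is true, but adjuvant therapy precedes randomization and is balanced between arms in expectation. Chemotherapy after recurrence has no such protection, and sampling after it is avoidable.
- **The analysis is exploratory, and multivariable models may be considered** (Section 11.3.2). Records of later therapy are collected (Section 2.2). Both are so, but no term for chemotherapy before biopsy is specified. The on-treatment plasma series in Arm A does not depend on this footnote.

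**Conclusion.** The point holds as an internal conflict with an unaddressed analytic consequence. On its literal wording, footnote 13 permits a research biopsy up to 28 − c days after the first chemotherapy dose whenever c is below 28. No other section prevents this or says how such a sample is analysed. The tissue-methylation endpoint can therefore be confounded in some patients.

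The documents do not support the stronger statement that the endpoint is confounded, or that the arms' comparison is biased. The number of affected biopsies is unknown, and the intervals of 21, 14 and 7 days rest on assumed values of c. The consequence is limited to an exploratory secondary endpoint; primary PFS, its error rate and the sample size are unaffected.

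**What to change.** Reconcile footnote 13 with its own first sentence and with Sections 5.4, 5.5, 8.2, 8.2.1.2 and 8.2.1.3, so that the research sample is meant to be a recurrence sample taken before chemotherapy. Keep the 4-week outer limit: a bare before-chemotherapy rule would have no end when chemotherapy is late or never given. The change concerns research sampling only and should neither alter nor delay treatment.

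Record the biopsy date and the first-dose date, and flag any sample taken after chemotherapy starts. In Section 11.3.2, prespecify the tissue comparison both with and without flagged samples. Exclusion should not be the only analysis, because it selects on an event after randomization and could itself unbalance the arms.

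The cost is a one-line amendment, a date check (therapy records are already collected under Section 2.2) and a short addition to the analysis text. Some late biopsies may fall outside the window, including those that the present wording allows after day 28 when chemotherapy starts late, and some may be set aside in the sensitivity analysis. The change from resection to recurrence will still include the effect of adjuvant therapy.
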